Non-invasive respiratory support includes: High Flow Nasal Cannula (HFNC) or nasal-only modes of non-invasive ventilation (CPAP or Nasal IMV or BiPAP). It does not include oxygen therapy via face mask, nasal cannula, oxygen hood, or blow by oxygen alone. Duration of NRS after extubation is defined as the number of days and hours that the patient is on NRS after extubation, censored at 60 days after study enrollment. For calculations, the end of NRS will be calculated as NRS being continuously absent for at least 24 hours. Resumption of NRS after 24 hours and subsequent periods of NRS within 60 days of study enrollment will be summed together to represent total duration of NRS after extubation.

6. Re-intubation within 48 hours of extubation- Secondary Outcome

Re-intubation will be defined as re-insertion of the endotracheal tube within 48 hours of the initial extubation. For tracheostomy patients, re-intubation is defined as re-initiation of positive pressure mechanical ventilation within 48 hours of discontinuation.

7. Re-intubation within 7 days of extubation- Secondary Outcome

Re-intubation will be defined as re-insertion of the endotracheal tube within 7 days of the initial extubation. For tracheostomy patients, re-intubation is defined as re-initiation of positive pressure mechanical ventilation within 7 days of discontinuation.

8. Ventilator Free Days- Secondary Outcome

Because the acute phase of ventilation is often long and less predictable, weaning duration was chosen as the primary outcome because there is more variability in Ventilator Free Days (VFDs) than in weaning duration. However VFDs is a secondary outcome. VFDs will be calculated at 28 and 60 days, defined as total number of days after initiation of MV in which the patient is alive and not on ventilation. The components of length of mechanical ventilation used for VFD calculations include length of IMV (2 above), length of NIV after extubation (3 above) and length of NIV prior to intubation (4) above. Patients who die within the 28 or 60 days will have 0 28 or 60 Day VFDs respectively.

9. Use and duration of rescue therapies - Secondary Outcomes

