Comparison (a) REDvent-acute versus control: A 1-day reduction in length of weaning is considered clinically significant (less sedative exposure, fewer nosocomial infections, lower healthcare costs). With a sample size of 276 patients (138 per arm), up to 12% mortality and 1% attrition or incorrect randomization, a minimum of 240 patients (120 per arm) will be available for analysis of the acute phase. Power is based on 2 planned methods for analysis: cox proportional hazard ratios for multivariable analysis and univariate analysis with an independent t-test using log transformation (as needed) to account for the expected distribution of weaning duration. For univariate analysis using the assumptions above, we would be able to detect a ≥ 1 -day reduction in weaning duration with an alpha of 0.05 and power of 0.9 (Figure 7). For the cox proportional hazard model, we would be able to detect a relative hazard ratio of 1.5 (ratio between control/intervention group) with a power of 0.9 or a hazard ratio of 1.4 with a power of 0.8.

Comparison (b) REDvent-weaning versus control: Patients who fail the initial SBT will undergo the weaning phase randomization. From our pilot data, approximately 25% of patients exposed to the intervention passed the initial SBT, corroborating previous studies.¹⁵ Thus, at least 180 patients (90 per arm) will receive weaning phase interventions. Using the same assumptions as above, we will be able to detect a ≥ 1 day

reduction in the length of the weaning phase (Figure 8), or a hazard ratio of 1.5 with an alpha of 0.05 and power of 0.8. Patients who do not pass the SBT by 28 days post the weaning phase randomization will be censored for analysis, as study interventions and daily monitoring will end on day 29.

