Secondary Outcomes for SA 1: The 28 and 60 Day Ventilator Free Days (28D VFD, 60D VFD) will be secondary outcomes of this aim. Groups for VFD analysis will be based on any exposure to the intervention (acute or weaning) because some patients will never undergo a weaning phase randomization (i.e. died or were extubated right after the acute phase). If patients who died as well as those who dropped out are included in the VFD analysis, with the assumptions above regarding expected passing rate of SBTs, the estimated distribution of patients in 3 distinct groups will be: (a) REDvent only (n=108); (b) REDvent and control (n=90); (c) control only (n=102). We anticipate children in the REDvent only arm will have the most 28 D VFDs (anticipation 22), and those in the control only arm the least (anticipation 20). Directly comparing control only patients to REDvent only patients, with an expected standard deviation for VFDs between 5 to 9 days, we will be able to detect a 2-day change in VFDs between groups with a power between 0.35 and 0.82. Re-intubation rates are expected to be 10%, allowing us to confirm that REDvent is not inferior to usual care in regards to re-intubation with a non-inferiority margin of 0.10 with a power of 0.8 and alpha of 0.05. Finally, to ensure that REDvent is promoting greater patient effort of breathing and that the intervention does not alter clinical practice in the usual care arm, we will compare time weighted average values for direct measures of patient effort of breathing (PRP, PTP, Diaphragm Contractile Activity), and ventilator settings between intervention and control groups, and monitor the separation between groups over the time of the study.

D.6.4.2 SA2 Analysis Plan: To determine if changes to direct measures of respiratory muscle strength, load, effort, and architecture throughout the duration of MV are related to weaning outcomes.

Analysis and Sample Size: The primary outcome of this aim is weaning duration (as defined above). For this analysis, we will compare how each respiratory measure detailed in the data collection table relates to weaning duration. For respiratory muscle

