- If the weaning phase is suspended for > 12 hours and the patient no longer meets weaning criteria, the acute phase intervention will be resumed, until the patient again meets weaning criteria. This will be labeled weaning failure, and tracked in both arms.

The table below summarizes all protocol changes and the dates the amendments were approved by the Children's Hospital Institutional Review Board. Changes related to conduct of the trial (modifications of inclusion and exclusion criteria, sample size etc) were approved by the DSMB and NHLBI. Minor changes related to additional surveys or additional funding for secondary analysis are also included in the table below but did not result in substantive changes to the conduct of the trial.

Amendment Date	Summary of Changes
10/10/2018	Exclusion criteria revised to allow inclusion of patients with tracheostomy without home mechanical ventilation. Protocol change approved by NHLBI and DSMB to help increase enrollment to stay aligned with milestone accrual plan.
5/30/2019	Inclusion of Health-Related Quality of Life questions (surveys) at ICU admit and Discharge (additional funding received)
10/14/2019	Sample size reduced from 300 to 276. Inclusion of Phillips NM3 volumetric capnography device (ancillary study funding). Protocol change approved by NHLBI and DSMB.
3/18/2020	COVID-19 related changes including allowing up to 72 hours from intubation for enrollment of all patients (previously restricted to those admitted from an outside ICU). This was to facilitate recruitment while staying compliant with institutional protocols related to COVID-19. Protocol change approved by NHLBI and DSMB.
08/08/2020	Addition of survey related to Vaping/Smoking exposure (ancillary study funding)
11/17/2022	Age range for inclusion increased from 18 to 21 years of age. Protocol change approved by NHLBI and DSMB to help increase enrollment to stay aligned with milestone accrual plan.
03/28/2023	Details added regarding secondary analysis related to patient-ventilator asynchrony (additional funding obtained).

REDvent Statistical Analysis Plan (Fall 2019)

Inclusion Criteria

1. Children > 1 month (at least 44 weeks corrected gestational age) and ≤ 18 years of age AND

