Received Non-invasive respiratory support (NRS) post-extubation (secondary outcome)	Yes/no binary variable for receiving NRS after successful extubation. NRS includes: High Flow Nasal Cannula (HFNC) or nasal-only modes of non-invasive ventilation (CPAP or Nasal IMV or BiPAP) Successful extubation is defined as no death or re-intubation within 24 hours of extubation.	Patients who die within 24 hours of IMV or remain on IMV at 90 days are not included.	Multivariable logistic regression controlling for blocking variables and confounders.	Adjusted odds ratio for receiving NRS post-extubation with 95% C.I. for REDvent vs. Usual care will be presented.	January 2024 added as necessary component to interpret length of NRS after extubation more appropriately.
NRS duration after extubation (secondary outcome)	Duration of NRS after extubation is defined as the number of days and hours that the patient is on NRS after successful liberation. End of NRS is defined as absent continuously for at least 24 hours. Successful extubation is defined as no death or re-intubation within 24 hours of extubation.	Patients who die within 24 hours of IMV or who never receive NRS post-extubation are excluded. Patients who remain on NRS at 90 days will have 90 days imputed. Patients who die while on NRS will have their death date as end of NIV duration.	Log transformed multiple linear regression controlling for blocking variables and confounders.	NRS duration will be expressed in days. Adjusted mean difference and 95% C.I. for REDvent vs. usual care will be back transformed with $\exp(\text{estimate})$ and interpreted as a relative change.	None
Re-intubation within 48 hours of extubation (secondary outcome)	Binary variable for re-insertion of endotracheal tube within 48 hours of initial extubation.	Patients who remain on IMV for their index intubation or die within 48 hours of index extubation are excluded.	Multivariable logistic regression for the event re-intubation = yes. Adjusting for blocking variables and confounders.	Binary yes/no variable. Adjusted odds ratio for re-intubation with 95% C.I. for REDvent vs. Usual care will be presented.	None

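### As worded, the SAP's 48-hour re-intubation row excludes a child re-intubated before an early death and omits the protocol's tracheostomy definition, so it can classify events differently from the protocol

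*Combined protocol and SAP*

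**What the plan says.** **SAP.** The July 2024 final SAP, Table 1, describes the outcome as: "Binary variable for re-insertion of endotracheal tube within 48 hours of initial extubation". Its exclusion column reads: "Patients who remain on IMV for their index intubation or die within 48 hours of index extubation are excluded". The Fall 2019 SAP has the same row, and the final SAP's column of changes records none. The planned result is an adjusted odds ratio from logistic regression.

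**Protocol.** Section C.3.1 item 6 of the current protocol states: "Re-intubation will be defined as re-insertion of the endotracheal tube within 48 hours of the initial extubation". It has no exclusion for death. It goes on: "For tracheostomy patients, re-intubation is defined as re-initiation of positive pressure mechanical ventilation within 48 hours of discontinuation". Items 1 and 2 of the same section define extubation and the end of intubation for these patients by removal of positive pressure ventilation.

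**Eligibility.** The amendment table records for October 2018: "Exclusion criteria revised to allow inclusion of patients with tracheostomy without home mechanical ventilation". The current exclusion criteria (D.2.2) and the exclusion lists of both SAPs do not name tracheostomy.

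**Role of the outcome.** Section D.6.4.1 expects a 10% re-intubation rate and plans to show that REDvent is not inferior to usual care, with a "non-inferiority margin of 0.10 with a power of 0.8 and alpha of 0.05".

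**The concern.** Excluding a child who dies within 48 hours makes sense when there was no re-intubation, because the 48-hour status was then never fully observed. It does not make sense when the tube went back in before the death. The event is then known, nothing is missing, and the protocol counts it. The exclusion as worded does not separate the two cases. It also depends on something that happens after randomisation, which fits poorly with the intention-to-treat statement in the final SAP.

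The tracheostomy gap is a conflict between documents. A programmer who follows only the SAP row looks for re-insertion of an endotracheal tube and finds none.

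Re-intubation is the safety counterweight to faster weaning. The children at issue in the first limb would be the gravest extubation failures, and the event count is small enough for single records to be visible in the estimate.

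**Working it through.** **1. The plan's own figure.** The only number stated for this outcome is the power of 0.8. With 10% in both arms, margin 0.10 and unpooled variance, n per arm = (z₁₋α + z₀.₈₀)² × 2 × 0.10 × 0.90 / 0.10².
- One-sided alpha 0.05: (1.645 + 0.842)² × 18 gives 112 per arm. With the 120 per arm of D.6.4.1, power is 0.826.
- One-sided alpha 0.025: (1.960 + 0.842)² × 18 gives 142 per arm. With 138 per arm, power is 0.791.

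The documents state neither the sidedness nor the N, but 0.8 is attainable. Removing 3 children per arm changes power only from 0.826 to 0.817 (120 per arm, one-sided 0.05). The issue is classification, not power.

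**2. Hypothetical records under each document.**

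| Record | Protocol C.3.1 item 6 | SAP Table 1 row as worded |
|---|---|---|
| Re-intubated at hour 8, alive at hour 48 | Event | Event |
| Re-intubated at hour 8, dies at hour 40 | Event | Excluded |
| Never re-intubated, dies at hour 40 | No exclusion stated; no tube re-inserted | Excluded |
| Tracheostomy, off ventilation at hour 0, back on at hour 20 | Event | No event, or undefined |

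The second and fourth records are the discrepancies.

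**3. Expected number of events.** Analysable children: 240 (D.6.4.1), or 0.87 × 230 ≈ 200 under the January 2023 minimum sample size with 13% not meeting the primary outcome. At 10%, that is 20 to 24 events.

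**4. Effect of losing events.** Start from 12/120 in each arm (12 events, 108 non-events). An excluded event leaves both numerator and denominator, so the non-events stay at 108 and the odds ratio is the ratio of remaining events.
- Lost in usual care: 12/11 = 1.09, 12/10 = 1.20, 12/9 = 1.33.
- Lost in REDvent: 11/12 = 0.92, 10/12 = 0.83, 9/12 = 0.75.
- The affected arm's rate falls from 10.0% to 9.2%, 8.5% or 7.7%.

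A tracheostomy failure scored as no event stays in the denominator. The rate becomes 9.2%, 8.3% or 7.5% for one, two or three such children. For one in usual care the odds ratio is (12/108)/(11/109) = 1.10.

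For scale, the 95% interval around 12/120 versus 12/120 is exp(±1.96 × √(2/12 + 2/108)), about 0.43 to 2.32.

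**5. How likely is a loss?** The documents give no count of children re-intubated and dead within 48 hours. If a fraction q of re-intubated children died before hour 48, with q assumed to be 0.02 to 0.10, expected losses are 20 × 0.02 = 0.4 to 24 × 0.10 = 2.4 over both arms. The chance of at least one is 1 − 0.98²⁰ = 33% to 1 − 0.90²⁴ = 92%. Three or more losses in one arm and none in the other, with 12 events per arm, has probability of about 0.2% (q = 0.02) to 6% (q = 0.10).

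**6. Could it matter for the margin?** Assumed true failures: 15/120 REDvent, 12/120 usual care. The difference is 2.5 points, with an upper two-sided 95% limit of 10.5 points. Dropping two REDvent failures gives 13/118, a difference of 1.0 point and an upper limit of 8.8. The 10-point margin is missed in the first case and met in the second. With a one-sided 95% limit the figures are 9.2 and 7.6, and the margin is met both times.

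**The case against.** **The protocol already covers tracheostomy.** This is right as far as it goes. A reader might infer from the SAP row that tracheostomy children can never be counted. The documents do not support that: C.3.1 items 1, 2, 6 and 7 define extubation and re-intubation for them. The SAP's other outcome rows carry no tracheostomy wording either, which suggests shorthand rather than a decision. What stands is that the row asks for an endotracheal tube and so conflicts with the protocol.

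**No harm is shown.** A reader might also infer that real extubation failures have been dropped or scored as no event. Nothing in the documents reports such a child. The clause may have been written only for death without re-intubation, but its wording is not limited to that case.

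**The effect is small and the deaths are counted elsewhere.** Both true. ICU and 90-day mortality have no exclusions, and a death within 28 days gives zero 28-day ventilator-free days. The larger odds-ratio shifts need all losses in one arm. But the mortality rows do not put a missing failure back into the re-intubation comparison, and the protocol's 7-day re-intubation outcome has no row in SAP Table 1.

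**It is late, and the fix still excludes some deaths.** The final SAP postdates unblinded analysis and the final DSMB meeting, so a redefinition now is post hoc and must be labelled. Excluding deaths without re-intubation is also a post-randomisation exclusion, which is why a sensitivity analysis belongs with it.

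**Conclusion.** The exclusion is wrong as worded. It removes a child whose re-intubation was observed within the window, where the protocol counts the event. The tracheostomy limb is a conflict between the SAP row and the protocol for a group eligible since October 2018.

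The likely size is small. One lost event in one arm moves an odds ratio of 1.00 to about 1.09 or 0.92, well inside an interval of roughly 0.43 to 2.32. That rests on the plan's 10% rate and 120 per arm. The chance of any loss (33% to 92%) rests on an assumed 2% to 10% early-death fraction among re-intubated children, and the number of tracheostomy children is not given. A change in the non-inferiority conclusion is possible only in borderline configurations such as the one in step 6, and there it depends on which confidence limit is used. The case for correction is that the rule contradicts the protocol on a safety outcome and is easy to put right.

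**What to change.** In the SAP Table 1 row for 48-hour re-intubation:

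1. Score any re-intubation within 48 hours of index extubation as an event, whatever happens afterwards.
2. Limit the death exclusion to children who die within 48 hours without re-intubation. Report their number by arm, and add a sensitivity analysis that counts them as failures.
3. Carry over the protocol's existing tracheostomy definition from C.3.1 item 6.
4. Because the final SAP postdates unblinded analysis, describe the change as alignment with the protocol definition, and show the result under the present SAP wording beside it.

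The cost is a few sentences in the table, re-derivation of one binary variable and a re-run of one model with its sensitivity analysis. Re-intubation and death are already recorded as trial outcomes. If no child is affected, one sentence saying so closes the point.

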For all variables, descriptive statistics will be calculated, including means, standard deviations, medians, and interquartile ranges for continuous variables and frequency counts and percentages for categorical variables. Data will be examined for skewness, outliers, and systematic missing data. Transformations will be undertaken as needed. Comparisons of demographic and baseline variables will be obtained by treatment group.

D.6.4.1 SA 1 Analysis Plan: To determine if REDvent acute and/or weaning phase protocols can shorten the duration of weaning from MV (Primary outcome).

Primary analysis and sample size: The primary outcome for this aim is weaning duration. Because we seek to understand whether REDvent-acute and/or REDvent weaning have an independent effect on length of weaning, we propose a sample size to adequately power 3 separate comparative analyses: **(a)** REDvent-acute versus Acute Phase control **(b)** REDvent-weaning phase versus Weaning Phase control **(c)** REDvent both phases versus control both phases. We expect up to 12% mortality before the first SBT based on our Preliminary Data. These patients will not be included in the analysis for the primary outcome. From our pilot data (REDvent in both acute and weaning phases), the duration of the weaning phase in the intervention arm was 2.2 days, compared to 4 days in historical controls with a standard deviation of 2.1 days in the intervention arm and 2.8 days in the historical controls.

[figure not shown]

Figure 8: Power curve for a 1 day reduction in weaning

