The revised milestone accrual plan has been reviewed and approved by the DSMB and NHLBI. Initial estimates of mortality and attrition were 13% and 7%, respectively, allowing for 20% of patients not meeting the primary outcome measure. Based on enrolled patients as of 08/16/2019, no patients have withdrawn from the study, and the overall mortality is 11.8%. As a result, the overall sample size estimate has been revised using 13% of patients who will not meet the primary outcome, rather than 20%. Target study enrollment of 300 total patients has been dropped to 276. The A-priori determination of 240 patients meeting the primary outcome measure has not changed.

[figure not shown]

Figure 8: Revised Milestone Accrual Plan

E Human Subjects Considerations

E1 Ethical Considerations

The human subjects for this study are infants and children who are intubated and mechanically ventilated in intensive care unit. It is anticipated that 276 intubated children will be enrolled in the study. The age of children will range from one month (\geq 44 weeks Post Conceptual Age) to 21 years. All participants enrolled in the study will be critically ill, requiring mechanical ventilation through an endotracheal or tracheal tube. The main risk of participation in this study is the placement of an esophageal catheter for measurements of esophageal pressure. While esophageal catheters (or nasogastric feeding tubes) are routinely used in children who are mechanically ventilated (it is the norm for all endotracheally intubated children to have a feeding tube, either nasogastric, orogastric, gastric, or jejunal), because this additional catheter is part of the research protocol, it is likely to be considered greater than minimal risk. However the study does provide potential for significant benefit for the patient, and as such the benefits generally outweigh the risks. Use of this catheter has been approved on multiple occasions with appropriate informed consent. The ultrasound measurements and RIP bands are non-invasive and pose minimal risk to the patient. There are no known risks associated with the use of volumetric capnography.

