Model assumptions and fit for multiple linear regression (with or without log transformation) will be assessed visually for normality of residuals as well as variance inflation factor and difference in betas (DFBETAS) for influential points. Model fit for binary multiple logistic regression will be assessed with Pearson Chi-square and deviance. Firth's penalized likelihood method will be used in subgroup analyses when event rates are small to reduce bias in the parameter estimates.⁴ When using negative binomial regression, model fit will be assessed for over and underdispersion with the scaled Pearson Chi-square/deviance and influential points assessed as previously described. The proportional hazards assumption will be assessed when using Cox proportional hazards modeling using graphical approaches ("log-log" figures and Kaplan-Meier curves) for each covariate. Repeated measures analysis for ventilator settings, lung mechanics, and respiratory measures will be assessed with linear mixed models and generalized linear mixed models that include a variable for time from randomization to control for correlation of values within each patient using the first-order autoregressive structure. The robust sandwich estimators for standard errors will be used to reduce heteroscedasticity when appropriate.

A detailed outline of each outcome's analysis approach to control for blocking variables and confounders is given in the Table 1. Pre-specified comparisons of interest are REDvent acute vs. usual care acute, REDvent weaning vs. usual care weaning, and four group combination: 1) REDvent acute + REDvent weaning 2) REDvent acute + usual care weaning 3) Usual care acute + usual care weaning 4) usual care acute + REDvent weaning. The four group combinations comparisons are exploratory and will only be considered if there are noted differences between both acute and weaning phase interventions.

October 2019- new milestone accrual plan

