28-day ventilator free days (secondary outcome)	Number of days between index intubation and 28-days post-index intubation in which patient is alive and not on IMV.	No exclusions.	Competing risks regression adjusting for blocking variables and confounders. Censoring indicators: 0=those who do not die but are not extubated within 28 days 1=those that have successful liberation within 28-days 2=those that die within 28-days	If patient is re-intubated within 24 hours of extubation the time in between intubations is not counted towards VFDs. If a patient is extubated for >24 hours and then subsequently re-intubated they get credit for those days without IMV. Values are 0 to 28 days. Adjusted hazard ratio and 95% C.I. will be presented.	January 2023- Updated competing risk regression to negative binomial model to align with analysis plan for primary outcome and because the variable is a count of the number of days. Negative binomial also treats death and those on IMV for 28 days as the same (zero VFDs). This aligns with the hypothesis that the influence of the treatment variable is on the days of ventilation, and we do not expect any treatment effect for death.
PiMax on day of 1st SBT (secondary outcome)	PiMax value on the day the 1 st SBT was performed.	Patient with values >100 will be truncated to 100. Exclude patients who never attempted an SBT in the 28-days study period.	Multiple linear regression adjusting for blocking variables and confounders.	Adjusted mean difference with 95% C.I. will be presented for REDvent vs. Usual care.	June 2024- unable to satisfy assumptions of linear regression with any transformation. Modeled as non-parametric proportional odds logistic regression.

PiMax on day of extubation (secondary outcome)	PiMax value on the day of extubation. Restricted to those who met primary outcome (SBT passage or successful extubation).	Patient with values >100 will be truncated to 100. Exclude patients who died within 24 hours of extubation or remained intubated at 90 days.	Multiple linear regression adjusting for blocking variables and confounders.	Adjusted mean difference with 95% C.I. will be presented for REDvent vs. Usual care.	June 2024- unable to satisfy assumptions of linear regression with any transformation. Modeled as non-parametric proportional odds logistic regression.

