Negative Binomial Model	Length of Weaning (initial plan- revised); Ventilator Free Days	Count variables with adjustment for blocking variables and confounders. Model assumptions and methods to evaluate model fit: Pearson Chi-square/deviance for over and under-dispersion, DFBETAS and variance inflation factor.	Raw estimate and 95% C.I. for REDvent vs. usual care exponentiated to obtain Incidence Rate Ratio with 95% C.I. Patients in the REDvent group had a decreased rate of length of weaning by x% compared to usual care after adjusting for blocking variables and confounders.
Logistic regression	First SBT success; re-intubation, NIV/NRS use post extubation; ICU and 90 day mortality; decline in PCPC or POPC;	Binary outcomes with adjustment for blocking variables and confounders. Firth's penalized likelihood method was used in subgroup analyses when event rates were small to reduce bias in the parameter estimates.	Odds Ratio with 95% C.I. Patients in the REDvent group had higher odds (if OR>1) of achieving the outcome than usual care after adjustment for blocking and confounding variables.
Linear Regression	Days to first SBT and SBT passage; length of IMV; length of NRS/NIV post extubation; ICU Length of Stay; Hospital Length of Stay	Continuous outcomes with adjustment for blocking variables and confounders. Residuals evaluated for normality, homoscedasticity. DFBETAS and variance inflation factors assessed for influence of observations. Log transformation of the outcome used when appropriate.	Relative change (slope) of regression coefficient with 95% confidence interval. Patients in the REDvent group had a reduction in length of IMV by x compared to usual care. If log transformation used the estimate for the adjusted mean difference and 95% C.I. on the log scale were exponentiated. Outcome decreased by x% in the REDvent group compared to usual care.

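### 28-day ventilator-free days are given a negative binomial model with no variance estimator that fits a capped outcome with a spike at zero; the default interval is about 1.1 times too wide at 3% zeros and about 1.6 times at 12%

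*Combined protocol and SAP*

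**What the plan says.** Final SAP (July 2024), Table 1, 28-day ventilator free days: no patient is excluded and values run from 0 to 28. The last column records the January 2023 change: "Updated competing risk regression to negative binomial model to align with analysis plan for primary outcome". Two further reasons are given there: the variable counts days, and the model scores death and 28 days of invasive ventilation alike, as zero.

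Table 2 of the final SAP lists the outcomes under the negative binomial model as "Length of Weaning (initial plan- revised); Ventilator Free Days". The fit checks named for it are "Pearson Chi-square/deviance for over and under-dispersion, DFBETAS and variance inflation factor". The SAP text on model assumptions repeats the dispersion check but does not say what follows if it fails.

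Robust variance appears once, in that same text: "The robust sandwich estimators for standard errors will be used to reduce heteroscedasticity when appropriate". The sentence comes directly after the one on repeated-measures mixed models and names no outcome. The SAP also allows nonparametric analysis at the analyst's discretion.

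The current protocol, D.6.4.1, Secondary Outcomes for SA 1, anticipates mean VFDs of 22 (REDvent only, n=108) and 20 (control only, n=102), with an SD of 5 to 9 days, and states that "we will be able to detect a 2-day change in VFDs between groups with a power between 0.35 and 0.82".

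**The concern.** VFDs are bounded at 28, left-skewed among survivors, and have a lump at 0. A negative binomial distribution with a mean near 20 can produce an appreciable share of zeros only with a large dispersion. Maximum likelihood therefore raises the dispersion to accommodate them, and the implied variance, mean plus dispersion times mean squared, exceeds the variance the data actually have. The standard error and confidence interval built on it are too wide. None of the three reasons given for the model bears on this.

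VFD is a secondary outcome here, but the protocol names it as a key clinical outcome for a later Phase III trial. An interval that is too wide can make a real gain, or a real harm, look like no difference.

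**Working it through.** **1. The protocol's own power figure.** Comparison of two means, two-sided alpha 0.05 (stated for the primary outcome, assumed here), difference 2 days, SE = SD × √(1/108 + 1/102). A t-test gives power 0.82 at SD 5 and 0.36 at SD 9, which matches the stated 0.82 and 0.35. The figure is therefore for a comparison of means, not for the negative binomial model.

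**2. Inputs for the variance check.** The documents give the range 0–28, the scoring of zeros, the anticipated means (20–22) and the SD (5–9). They do not give the day-28 share of zeros. The nearest figures are in the current protocol, D.6.4.1 ("We expect up to 12% mortality before the first SBT based on our Preliminary Data") and D10 ("no patients have withdrawn from the study, and the overall mortality is 11.8" per cent, August 2019). Neither is the quantity needed: some deaths may fall after day 28, while survivors ventilated for all 28 days add zeros. The share is therefore an assumption, shown from 3% to 12%. The survivor distribution is also an assumption.

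**3. Large-sample calculation.** VFD = 0 with probability p, otherwise a discretised scaled beta on 1–28 with survivor mean 22 and SD 4. With μ and Var the mean and variance of the mixture, and a the maximum-likelihood dispersion:

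model SE / true SE = √[(μ + aμ²) / Var]

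Pearson/df ≈ Var / (μ + aμ²)

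| Zeros | μ | SD | a | SE ratio | Pearson/df |
|---|---|---|---|---|---|
| 3% | 21.34 | 5.45 | 0.032 | 1.10 | 0.83 |
| 5% | 20.90 | 6.19 | 0.088 | 1.24 | 0.65 |
| 8% | 20.24 | 7.10 | 0.208 | 1.45 | 0.48 |
| 12% | 19.36 | 8.08 | 0.418 | 1.64 | 0.37 |

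At 12%, in numbers: μ + aμ² = 19.36 + 0.418 × 374.8 = 176.0; Var = 65.3; √(176.0/65.3) = 1.64. The dispersion that would match the actual variance is (65.3 − 19.36)/374.8 = 0.12, so the fitted value is more than three times too large.

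Over survivor means of 20–25 and SDs of 2.5–6, the ratio is 1.00–1.18 at 3% zeros and 1.53–1.77 at 12%.

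**4. Simulation with covariates.** 1,500 replicates per scenario, at 108 vs 102 and 115 vs 115, adjusted for age group and immunosuppression. Survivors' ventilator days were lognormal (mean about 6.5, CV 0.69); immunosuppression was set at 33%, with 2.6 times the risk of a zero and 15% longer ventilation. The intended VFD gain was 2 days (1.93–1.99 achieved).

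| Zeros | SD | SE ratio | Type I error, model SE | Power, model SE | Power, robust SE |
|---|---|---|---|---|---|
| 3% | 5.6 | 1.10–1.13 | 3.3% | 0.60–0.63 | 0.69–0.73 |
| 5% | 6.3 | 1.24–1.28 | 1.5–1.8% | 0.39–0.41 | 0.59–0.61 |
| 8% | 7.1 | 1.37–1.43 | 0.9% | 0.20–0.21 | 0.48–0.49 |
| 12% | 8.1 | 1.59–1.60 | 0.2% | 0.08–0.09 | 0.37–0.43 |

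Type I error with a sandwich or Pearson-scaled SE was 4.1–5.7% throughout. At 12% zeros and 108 vs 102, the upper 95% limit lies about 21% above the estimate instead of 13%. With 8 points more zeros under REDvent (8–12% in control), the harm is detected in 2–5% of trials with the model SE and 29–37% with the robust SE.

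**5. Sample size behind the stated power.** The D.6.4.1 groups sum to 108 + 90 + 102 = 300, but the target is now 230–276 (final SAP, January 2023 change). Scaling by 276/300 gives 99 vs 94 and power 0.34–0.79. Scaling by 230/300 gives 83 vs 78 and power 0.29–0.72 (0.71 by the t-test).

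**The case against.** The strongest reply is that the interval is too wide only if the analyst keeps the default standard error. The SAP names under-dispersion as a diagnostic for this very model, permits sandwich errors and nonparametric methods, and records that the team changed models in 2024 when diagnostics failed for length of weaning and PiMax. That shows a correction was possible, not that one was planned. Nothing ties the check to an action, and no 2024 change is recorded for VFDs.

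The size does rest on a zero share and a survivor distribution that the documents do not give, and at 3% zeros there may be almost no inflation. Nor does the ratio fall steadily to 1 below 3%: with no zeros and survivor SD 4 it is 1.17, because the dispersion cannot go below the Poisson value. It may also be said that 12% zeros implies a mean below the anticipated 20–22. That depends on the survivor shape: survivor mean 24 and SD 3 with 12% zeros gives mean 21.1, SD 8.3 and a ratio of 1.73, inside the protocol's ranges for both mean and SD.

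Hidden harm is partly covered elsewhere, since ICU mortality, 90-day mortality and duration of invasive ventilation have their own analyses. This limits the consequence but leaves the VFD interval wrong. Finally, a post-unblinding change that narrows an interval can alter a conclusion, so it needs open disclosure.

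**Conclusion.** The concern holds and should be fixed. As written, the SAP leaves VFD inference on a negative binomial variance that does not suit the outcome, and its safeguards are discretionary. The direction is secure from 3% to 12% zeros; the size is conditional on the assumed zero share and survivor distribution. The loss is small near the low end of the protocol's SD range and large at an SD of about 8. The mortality figures in the documents lie nearer the upper end of the zero range, though they do not establish the day-28 share. The error is conservative and concerns one secondary outcome, so it does not threaten the primary result. Separately, the stated VFD power describes neither the current model nor the current sample size.

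**What to change.** In Tables 1 and 2 of the final SAP, state that VFD inference uses a sandwich or Pearson-scaled standard error. The ratio of means may stay; report beside it the mean difference in days with a bootstrap interval.

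The proportional odds model already used for other outcomes (ordered 0–28, death as 0, same covariates) can be added as a sensitivity or co-reported analysis. It should not replace the comparison of means, because the power of a rank-based method depends on where the benefit falls. In an unadjusted check with 12% deaths, Mann-Whitney power was 0.92 when every survivor gained 2 days but 0.13 when only stays over 8 days shortened, against 0.33 and 0.23 for the robust negative binomial. No proportional odds model was fitted.

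Restate the VFD power for the method, comparison and N actually used.

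The cost is two table cells, one re-run and one power sentence. Date the change and disclose that it came after unblinded diagnostics began in May 2024, giving the model-based interval alongside the robust one. The point estimate does not move, which keeps the credibility cost small provided both intervals are shown.
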